7.3 Assignment of treatment

The assignment/randomization of the treatment will be carried out centrally using a validated electronic system from an external provider, previously evaluated and authorized by Laboratorios Sophia S.A. de C.V. There are two treatment groups. Participants will be randomized in a 1:1 ratio to treatment with PRO-231 or VIGAMOXI.® Having the same probability of being assigned to one or the other treatment. After signing the FCI, the subject will receive a participant number with which all their information will be encrypted pseudonymity during collection and completely anonymized during analysis. The generation will be carried out by a third party, authorized by Laboratorios Sophia, S.A. de C.V., through its electronic system, through a list of random numbers generated by software (SAS Institute Inc, Cary, NC, USA). The information pertaining to this third party will be on file. Only the principal investigator and the person responsible for the statistical analysis will be blinded, because the primary packaging of the comparator cannot be modified to resemble the product under investigation. Despite this, the secondary packaging for the products will be the same and the researcher will not know the allocation. IP will be identified by means of labels in accordance with current and applicable regulations, which must contain at least:

- Sponsor's name, address, and phone number.
- Dosage form and route of administration.
- Number of doses.
- Batch number.
- Legend "Exclusively for clinical studies".
- Expiration date.

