7.4.4.6 Adverse events

As described in the [8. Evaluation and management of adverse events](#) An adverse event is defined as any unfavorable medical occurrence in a subject to whom an investigational product is administered, regardless of causal attribution.

Adverse event management shall be carried out as described in section [8. Evaluation and management of adverse events and incidents](#).

The Principal Investigator will record in the corresponding section of the eCRF the adverse events that the study subjects may present in addition to referring them in the clinical record.

For an adequate evaluation of adverse events, in addition to directed questioning, it is necessary to perform a comprehensive ophthalmological evaluation at each visit, which consists of: ophthalmological examination of the eyelids and adnexa; anterior and posterior segment that is performed in a routine ophthalmological check-up, whose procedures are not specifically included in the study variables. Posterior pole evaluation can be with direct or indirect ophthalmoscopy, with or without pharmacological mydriasis, at the discretion of the PI. An assessment of the fundus will be carried out in search of abnormalities that alter the result of the study. IOP will be measured in this evaluation, with the Goldmann tonometer, it should be measured after the evaluation of stains. The result of the assessment will be recorded in the clinical file. In the eCRF, only findings that are considered so by the Principal Investigator will be reported as an adverse event.

The ocular adverse events that can occur with PRO-231, according to what is reported in the literature, are: ocular burning, dysgeusia after instillation, foreign body sensation, ocular pruritus, conjunctival hyperemia, chemosis, photophobia and whitish corneal precipitates. The frequency of systemic adverse events with ophthalmic fluoroquinolone administration is low.[\[1, 13\]](#) [\[1\]](#)

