8.5.1 Recording of adverse events in the electronic case report form

The adverse event registry considers:

- Subject identification information such as: subject number, age, gender, and if applicable specify the eye.
- Information about the causality of the adverse event, its relationship to investigational products, or to another drug related to the study, as appropriate.
- Important date information:
 - Date on which the adverse event occurs.
 - Date on which the Principal Investigator becomes aware of it.
 - Date of resolution or outcome, as applicable.
- Information on diagnosis and clinical management.
- Record the outcome or resolution of the event:
 - Recovered/resolved
 - Recovered/resolved with sequelae
 - Recovering/Resolving
 - Not Recovered/Unresolved
 - Subject who presented death due to the adverse event
 - Subject who presented death and it is judged that the research product may have contributed
 - Subject who presented death and this is not related to the product under investigation
 - Unknown
- Information about the investigational product or product associated with the Adverse Event, Incident, Adverse Incident, AMR or SRAM must be recorded. The information essential for registration is the generic name, distinctive name or code of the investigational product or of the product associated with the undesirable clinical manifestation; it will also be necessary to enter the data concerning the batch number, manufacturing laboratory, expiration date, dose, route of administration, start and end dates of administration and/or consumption, reason for

prescription; according to whether it is an investigational product or drug (protocol in which the subject currently participates) or whether it is a drug that the research subject consumes for the treatment of underlying concomitant diseases or uses for the management of some transitory sign or symptom that does not correspond to the Natural History of the pathology that motivated its entry into the research protocol.

- Indicate whether the removal of the suspected product (of causing the event) eliminates the adverse event. Also indicate if a dose adjustment is made, if the event changes in terms of intensity or seriousness, persistence of the reaction. It is important to indicate whether in those subjects who are exposed again to the product, which had previously been suspended, the AD reappears.

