4. Taking the clinical information collected, either during the care provided at the research center or that provided by the treating physician(s) in the hospital, the PI will record the AE in its clinical note, stating the seriousness, intensity (mild, moderate or severe) and relationship with the investigational product.

5. The PI must migrate the relevant data to the eCRF and its respective adverse event section. By virtue of the fact that, in cases of serious adverse events, the clinical monitor of the study must be notified within 24 hours after learning of it, so that in turn it informs the Clinical Team and the Pharmacovigilance and Technovigilance Unit of Sophia Laboratories (UFTLS), and that the CEI/CI is subsequently notified. Non-serious adverse events will be recorded and treated appropriately and the safety profile of the investigational drug or drug will be reported to the appropriate regulatory authority in the final report of the clinical trial.

The recording of the outcome of the AE depends substantially on the follow-up that the Principal Investigator performs on the subject, since it is expected that most of the harmful phenomena (see subsection 2.5 Risk-benefit assessment and consult the Investigator's Manual) are ophthalmic in nature, however, there may be systemic alterations. Therefore, in the opinion of the researcher, the withdrawal of the participant or their permanence will be considered.

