8.5.4 Causation assessment

Causality assessment is the methodology used to estimate the probability of attributing the observed adverse event to a pharmaceutical product. It considers probabilistic categories according to the available evidence and the quality of the information, based on the national pharmacovigilance and technovigilance regulations, the World Health Organization and the Uppsala Monitoring Center. [33][51]

An adverse event may or may not be related to the clinical trial. A causal relationship means that the intervention caused (or is reasonably likely to have caused) the adverse event. This usually implies a relationship between the time of the intervention and the adverse event (e.g., the adverse event occurred shortly after the subject under investigation received the intervention). [49]

For all adverse events, the Principal Investigator is responsible for examining and evaluating the subject to determine the association of the event with the clinical study and the intervention, whether related to the experimental treatment, concomitant, surgical procedure, or diagnostic procedures performed during the study. [49]

Accepting that the adverse event is related to the clinical study requires a plausible mechanism of action, that is, that there is a logical sequence between the event that occurred and the intervention that caused it. In some cases, it is helpful to know the opinion of other doctors directly or indirectly involved in the research; as well as whether the subject considers that a relationship exists or not. [49]

UFTLS may employ the causation categories described by *the Uppsala Monitoring Centre*, to categorize the likelihood of adverse event to the investigational product or concomitant treatments or treatments used during visits: [33] [51]

- Definitive (certain): a clinical event, including alterations in laboratory tests, that manifests itself with a plausible temporal sequence in relation to the administration of the drug, and that cannot be explained by concurrent disease, or by other drugs or substances. The response to drug withdrawal (withdrawal) must be clinically plausible. The event must be definitive from a pharmacological or phenomenological point of view, using, if necessary, a conclusive re-exposure (challenge) procedure. [33] [51]

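### The adverse event record requires the product's manufacturer, which differs by arm, so a principal investigator who follows sections 7.4.4.6, 8.5.1 and 8.5.3 as written loses the mask for subjects with an adverse event

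*Combined protocol and SAP*

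**What the plan says.** On masking, section 7.3 states: "Only the principal investigator and the person responsible for the statistical analysis will be blinded". Sections 4.2 and 7.3 give the reason: the comparator's primary pack cannot be made to look like the test product. The only safeguard named is a common outer pack, so that "the secondary packaging for the products will be the same and the researcher will not know the allocation".

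On AE records, section 8.5.1 lists the product information to be held. The product may be identified by "generic name, distinctive name or code of the investigational product", and then "it will also be necessary to enter the data concerning the batch number, manufacturing laboratory, expiration date, dose" and further items. The option of a code is given for the product's name; none is given for manufacturer or batch.

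On who does this, section 7.4.4.6 says: "The Principal Investigator will record in the corresponding section of the eCRF the adverse events". Section 8.5.3, step 5, says: "The PI must migrate the relevant data to the eCRF and its respective adverse event section". Section 10.2 uses the principal investigator as its example of a user with data-capture access. Section 7.8.2 lets study team staff transcribe into the eCRF from source documents, but treats everything captured there as approved by the investigator.

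On causality, section 8.5.4 says: "For all adverse events, the Principal Investigator is responsible for examining and evaluating the subject to determine the association of the event". Section 8.5.3, step 4, has that judgement written in the clinical note, before the eCRF step.

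**The concern.** Subjects are not masked, so the principal investigator's mask is the only protection against assessor bias in the primary safety variables. One of these, the incidence of unexpected AEs related to the interventions, depends on that investigator's causality judgement (sections 7.4.1.1 and 7.4.3). The same investigator records the grades or presence of hyperemia, chemosis and corneal staining (sections 7.4.4.1, 7.4.4.2 and 7.4.4.5).

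A record-keeping rule that discloses the arm works against section 7.3, and it does so selectively, in the subjects who have had an AE. If causality is revised, or the eye graded again, with the arm known, the comparison of the two products on these variables is no longer a masked one for those subjects.

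**Working it through.** The plan has no figure to reproduce on this point, so the check sets the sections side by side.

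1. **Does the field identify the arm?** The test product is made by the sponsor (section 6.1.1) and the comparator by another company (section 6.1.4). With two arms and two manufacturers the correspondence is one to one, so a completed manufacturer field is the allocation.
2. **Does batch number do the same?** Only for someone who knows which batch belongs to which product. Batch is also on the label (section 7.3). The manufacturer field is the one that decides the matter.
3. **Does the principal investigator see the field?** Sections 7.4.4.6 and 8.5.3 name that person as the recorder. If staff transcribe instead, section 7.8.2 still counts the data as investigator-approved. No section hides the field, assigns it to an unmasked person or sets a masked convention for it.
4. **What is judged after disclosure?** Using the order of steps 4 and 5 in section 8.5.3 and the visits in section 7.6.2 (day 3, day 8, telephone call on day 12):
   - First causality judgement on a subject's first AE: written in the note before eCRF entry, so not exposed if the order is kept.
   - Revision of that judgement after eCRF entry: exposed.
   - A further AE in the same subject, for example at day 8 or at the day 12 call: exposed.
   - The reading that gave rise to the AE: made before the AE record exists, so not exposed.
   - Day 8 grades after an AE recorded at day 3: exposed.
   - Grades after an AE first recorded at day 8 or later: none is scheduled.
   - Subjects with no AE: not exposed by this route.
5. **How many subjects could have an AE record?** Section 10.1.1 cites at least one AE in 3 of 62 moxifloxacin-treated subjects and plans on 50% for PRO-231.
   - With 3/62 in both arms: 38 × 3/62 = 1.8 subjects.
   - With 50% in the test arm and 3/62 in the comparator arm: 19 × 0.50 + 19 × 3/62 = 9.5 + 0.9 = 10.4 subjects.

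   The range is therefore about 2 to 10 of 38. It is a ceiling on those exposed, since step 4 requires something further to be judged after the record is made. The 50% is a conservative planning value, and the 3/62 comes from a comparative trial against besifloxacin, not from this study's healthy volunteers.

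**The case against.** The best defence is that the plan never tells the principal investigator to unmask. Section 7.8.2 allows team staff to enter eCRF data, section 7.1 allows delegation to a pharmacist or coordinator, and section 8.5.1 lists what a record contains without saying who fills in each item. Section 8.5.3 also puts the causality judgement in the note first. A well-run site could keep the mask under this text.

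Much of this stands. It removes the first causality judgement from the concern and shows that a compliant route exists. It does not remove the conflict: two sections name the principal investigator as recorder, investigator approval extends to all captured data, and nothing reserves the manufacturer field for someone else.

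A reader might go further and infer any of the following, which the documents do not support:

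- *That every causality judgement is made with the arm known.* The order of steps 4 and 5 says otherwise for the first one.
- *That the hyperemia, chemosis or staining reading that triggers an AE is affected.* It precedes the record.
- *That batch alone unmasks.* It does so only with knowledge of the batch-to-product link.
- *That the principal investigator handles or weighs the bottles.* No section assigns dispensing or weighing to that role. The difference in bottles is openly given as the reason for limited masking.
- *That a p-value shift measures the harm.* At 17 per arm, moving from 5 versus 0 to 4 versus 0 related events moves Fisher's exact p from 0.044 to 0.103. Any single reclassification would do this, masked or not. It shows the fragility of a small sample, not bias from unmasking.

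**Conclusion.** The concern holds in a limited form. Sections 4.2 and 7.3 are not reconciled with section 8.5.1: following the AE recording rules as written discloses the allocation of a subject with an AE to the one clinical assessor who is meant not to know it. The exposure covers causality revisions, later AEs and later graded examinations of that subject, with day 8 after a day 3 AE as the clearest scheduled case.

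This rests on three assumptions: that the manufacturer field is completed for the study product, when section 8.5.1 also covers other suspected or concomitant products; that the principal investigator enters or reviews it; and that no separate document not seen here, such as eCRF completion guidelines, already restricts it. The number of subjects involved is probably small, and neither the direction nor the size of any bias can be stated from the documents. It should be corrected before enrolment because the affected judgements are primary variables and the correction is simple.

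**What to change.** In section 8.5.1, state that:

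- manufacturer and batch, and the product name unless a masked code is used, are completed from the randomisation system or by an unmasked delegate already on the delegation log;
- these eCRF fields are not visible to the principal investigator until database lock;
- the principal investigator records causality, and any revision of it, without them.

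In section 7.8.2, state that the investigator's approval of captured data excludes these fields; otherwise the restriction contradicts the approval rule. Add an exception for unmasking when a subject's safety requires it, with the date and reason recorded so that later assessments of that subject can be identified.

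As an optional clarification, the same delegate could be named for dispensing, collecting and weighing bottles, and subjects asked not to show or name the product to the principal investigator.

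The cost is setting up eCRF access rights, a few sentences in the protocol and delegation log, and some delegate time for each AE. All pharmacovigilance data are still collected, and no dose, visit, endpoint or sample size changes.

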7.4 Outcome variables

7.4.1 Primary outcome variables

7.4.1.1 Security

- Incidence of unexpected AEs related to interventions.
- Incidence of conjunctival hyperemia and chemosis.
- Changes in the AVMC evaluated with the Snellen chart.
- Changes in ocular surface integrity using fluorescein staining, using the Oxford scale.

7.4.1.2 Tolerability

- ICO score changes.

7.4.2 Secondary outcome variables

7.4.2.1 Security

- Incidence of expected and intervention-related AEs (excluding conjunctival hyperemia and/or chemosis).

7.4.2.2 Tolerability

- Presence of eye symptoms (burning, foreign body sensation, pruritus and tearing).

7.4.3 Definition of variables, methods and scales for their measurement

Board 2. Operational definition of variables

Variable	Conceptual Definition	Operational Definition	Measurement Type	Reference value	Statistical test
Incidence of Intervention-Related Unexpected AEs	Any adverse medical event that occurs in the clinical research subject to whom any of the interventions were administered and that has a certain coincidental relationship to the interventions [33]	All AEs (according to protocol) in which the PI suspects a causal relationship with the interventions will be reported	• Discrete quantitative • Nominal qualitative	• Relationship with IP • Severity • Causality	
 • Student's t-test of independent groups • U de Mann Whitney* • Pearson X² or Fisher Exact*
Incidence of conjunctival hyperemia	It is the reaction of the conjunctiva to a stimulus, a red appearance secondary to the vasodilation of the conjunctiva vessels of variable intensity is seen	Direct observation. Classification by Efron scale. See attachment 16.2. Efron Scale for Conjunctival Hyperemia	Degrees: 0 = Normal, I = Muy live, II = Mild, III = Moderate and IV = Severe		
 • Pearson X² or Fisher Exact* • McNemar Test*
Incidence of Chemosis	It is defined as conjunctival edema, the result of an inflammatory reaction. It is classified as present or absent	The evaluator will use a narrow beam of light at 60° and will measure whether the conjunctiva separates ≥ 1/3 of the total	• Nominal qualitative	Present / Absent	
 • Pearson X² or Fisher Exact* • McNemar Test*

Variable	Conceptual Definition	Operational Definition	Measurement Type	Reference value	Statistical test
Changes in the AVMC	Visual spatial acuity is the ability to distinguish separate elements of an object and identify them as a whole. It is quantified as the minimum angle of separation (located at the nodal point of the eye) between two objects that allows them to be perceived as separate objects	eyelid opening or if it exceeds the gray line Cartilla de Snellen. Ver anexo 16.5 Fraction to LogMAR conversion table.	• Continuous quantitative	20/30 (0.2 LogMAR) or better	
 • Student's t-test of independent groups • U de Mann Whitney*
Changes in the integrity of the ocular surface	Detection of corneal and conjunctival epithelial defects by means of the CT using the Oxford scale	Direct observation with slit lamp, graduation on Oxford scale. See attachment 16.3 Oxford scale	• Ordinal qualitative	Degrees: The TF is presented in a series of panels (A – E). The staining points vary from 0 – 5 for each panel and from 0 – 15 for the total exposed area of the conjunctiva and cornea	
 • Pearson X2 or Fisher Exact* • McNemar Test*
ICO score changes	The ICO is a questionnaire designed to measure irritation of the ocular surface, it assesses symptoms focused on the comfort associated with ocular surface alterations. Elevated values indicate more severe symptoms	The evaluator will apply the questionnaire to the subject and allow the subject to answer it calmly without any pressure and/or coercion. See annex 16.4 Eye Comfort Index (JI)	• Continuous quantitative	0 – 100	
 • Student's t-test of independent groups • U de Mann Whitney*

Variable	Conceptual Definition	Operational Definition	Measurement Type	Reference value	Statistical test
Incidence of expected and intervention-related AEs (excluding conjunctival hyperemia and/or chemosis). (bis)	Any adverse medical event that occurs in the clinical research subject who was administered any of the interventions and that has a causal relationship to them [33]	All intervention-related AEs will be reported according to the protocol.	• Discrete quantitative • Nominal qualitative	• Incidence • Severity • Causality	
 Independent group student's t-test U de Mann Whitney* Pearson X² or Fisher Exact*
Incidence of eye symptoms (burning, SCE, pruritus, and tearing)	
Burning: refers to the sensation of stinging or eye irritation.
 
SCE: refers to the sensation of "sand" inside the eye.
 
Pruritus: This refers to the itching or tickling sensation caused by the need to rub or scratch.
 
Tearing: It refers to excessive tear production [34, 35, 36, 37]
	The evaluator will perform the interrogation to rule out or confirm the general presence of symptoms	• Nominal qualitative	Present / Absent	
 Pearson X² or Fisher Exact* McNemar Test*

Abbreviations: AVMC, best corrected visual acuity; AE, adverse event; ICO, eye comfort index; IP; principal investigator; SCE, foreign body sensation; TF, fluorescein staining; X², Chi-square. *When applicable.

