- Incidence of conjunctival hyperemia and chemosis. (TE: day 3 and 8)
- Changes in the AVMC evaluated with the Snellen chart. (TE: day 3 and 8)
- Changes in ocular surface integrity using fluorescein staining, using the Oxford scale. (TE: day 3 and 8).

Tolerability

- ICO score changes. (TEE: day 8)

Secondary outcome variables:***Safety:***

- Incidence of expected and intervention-related AEs (excluding conjunctival hyperemia and/or chemosis). (TE: day 3, 8 and 12)

[figure not shown]
Tolerability:

- Presence of eye symptoms (burning, foreign body sensation, pruritus and tearing). (TE: day 3 and 8)

Statistical methodology

The analysis of the data collected in the study will be carried out by means of specialized statistical software (SPSS available version or R software). The data will be expressed with measures of central tendency: mean, standard deviation and/or ranges for quantitative variables, and frequencies and/or percentages for qualitative variables. The Shapiro-Wilk test (S-W) will be used to determine if the distribution is normal in the data obtained in each study group ($p>0.05$). If the normality in the distribution of the data is verified, to rule out differences between groups, the Student's t-statistic will be used for independent groups, while intragroup differences will be analyzed with the Student's t-test for repeated measures. In case of $p<0.05$ in S-W, the statistical analysis to rule out differences between groups will be performed by means of the Mann-Whitney U test for quantitative variables, while intragroup differences will be performed by Wilcoxon's rank test. The difference between the qualitative variables will be analyzed by means of the χ^2 statistic (Chi-squared) or Fisher's exact (for expected values less than 5). Dichotomous variables will be analyzed by the McNemar test when applicable. An alpha (α) ≤ 0.05 will be considered as statistical significance, in addition to this, the 95% CI will be calculated for these differences. For primary outcome variables, H_0 will be rejected, when $p \leq 0.05$ and the 95% CI does not include zero.

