10.3.1 Population Analysis

The statistical analysis will be presented to give a general summary of the subjects entered into the study and a view of the safety and tolerability of its results. The data provided by the research site will be summarized for this purpose, according to its nature. The Shapiro-Wilk test will be performed to find out if the quantitative data are distributed in a normal way ($p>0.05$).

The results of the quantitative variables will be presented in measures of central tendency: mean, standard deviation and/or ranges. Changes in the AVMC and ICO will be expressed as continuous variables. Whereas, the incidence (number) of AEs will be expressed as a discrete variable.

The result of the nominal and ordinal qualitative variables will be presented in frequencies, proportions and/or percentages. For these, tables of frequencies $p \times q$ will be constructed. All percentages will be presented with a decimal.

The level of difference to consider significance will be an alpha (α) of 0.05 or less, the 95% CI will be calculated for these differences. The triangulation between the type of variable and the measurements is shown in Table 5. [63]

The operational definition of the study for hypothesis testing will be as follows:

Hypothesis testing	value	Result	Interpretation
P value	≤ 0.05		
95% CI	Does not include zero	H_0 rejected	Both treatments are different in terms of safety and tolerability
P value	≥ 0.05	H_0 accepted	Both treatments are similar in terms of safety and tolerability (they are not different)
95% CI	Includes zero		

Both conditions for hypothesis testing (p-value and 95% CI) must be met, otherwise the result will be interpreted as "**absence of evidence**", not as "**evidence of absence**".

Board 5. Triangulation of concepts.

Variable Type	Variable	A1	A2	B1	C1	C2	C3	C4	D1	E1	F1	F2	F3	F4
Selection														
A1	Demographic			D										
A2	Medical History/Selection Criteria				D									
Basal														
B1	Comprehensive ophthalmological evaluation			T	D	TB	TB	B	T		TB			
Primary Security														
C1	Incidence of unexpected-related AEs				TB					TB				
C2	Incidence of conjunctival hyperemia and chemosis			T		TB				TB				
C3	AVMC			B	TB			B		TB				
C4	Corneal and conjunctival stains with fluorescein			B	TB			B		TB				
Primary Tolerability														
D1	ICO								B					
Secondary Security														
E1	Incidence of AE*			T			TB							
Secondary Tolerability														

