10.3.2 Safety and tolerability analysis

10.3.2.1 Analysis for Primary Variables

The analysis of the primary outcome variables of safety and tolerability will be carried out in the per-protocol population (PP), defined as any subject with an adherence $\geq 80\%$ determined by the subject's diary and corroborated by the final weight of the research product to which it was assigned (PRO-231 or VIGAMOXI)[®] with respect to its initial weight. and that they conclude their participation without deviations from the study protocol.

The Shapiro-Wilk test (S-W) will be used to determine if the distribution is normal in the data obtained in each study group ($p>0.05$). If the normality in the distribution of the data is verified, to rule out differences between groups, the Student's t-statistic will be used for independent groups, while intragroup differences will be analyzed with the Student's t-test for repeated measures.

In case of $p < 0.05$ in S-W, the statistical analysis to rule out differences between groups will be performed by means of the Mann-Whitney U test for quantitative variables, while intragroup differences will be performed by Wilcoxon's rank test.

For qualitative variables, Pearson's X² (Chi-square) or Fisher's exact test will be used in expected values less than 5. Dichotomous variables will be analyzed by the McNemar test when applicable.

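### Oxford staining, an ordinal primary safety variable, has no between-arm test that uses grade order, no named difference for the confidence-interval rule, and a Table 2 score that is never recorded

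*Combined protocol and SAP*

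**What the plan says.** The Synopsis lists the variable among the primary safety outcomes with two assessment days: "Changes in ocular surface integrity using fluorescein staining, using the Oxford scale. (TE: day 3 and 8".

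In Table 2 (7.4.3) the row is typed "Ordinal qualitative". The tests assigned, where applicable, are "Pearson X2 or Fisher Exact" and McNemar. The reference-value column describes staining points running "from 0 – 15 for the total exposed area of the conjunctiva and cornea". Table 5 (10.3.1) labels the same variable "Corneal and conjunctival stains with fluorescein".

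Section 10.3.2.1 provides the "Mann-Whitney U test for quantitative variables" when normality fails. It sends qualitative variables to chi-square, or to Fisher when expected values are below 5, and gives McNemar to dichotomous variables.

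Under 3.2 and 10.3.1, similarity is rejected when p is at most 0.05 and the 95% CI excludes zero. It is accepted when p is not significant and the CI includes zero. 10.3.1 adds: "Both conditions for hypothesis testing (p-value and 95% CI) must be met, otherwise the result will be interpreted as" inconclusive. On the interval itself it says only that "the 95% CI will be calculated for these differences".

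Section 7.4.4.5 has stain assessed in the cornea and one corneal grade, 0 to V, entered in the file and eCRF. Annex 16.3 gives the same single scale. Grade III or above is handled as an adverse event.

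**The concern.** Three gaps meet in one primary variable.

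- **Test.** The scale is ordered, but neither assigned procedure compares the arms using that order. Chi-square and Fisher treat grades as unordered labels. McNemar is paired and dichotomous, so it is not a between-arm test.
- **Interval.** The rule needs a signed difference with null zero. A table of several grades does not supply one, and neither a cut-off nor another measure is named. It would have to be chosen after the data are seen.
- **Score.** Tables 2 and 5 describe a corneal-plus-conjunctival quantity that the recorded data cannot produce.

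A non-significant p with an interval covering zero is read as similarity. An insensitive test, or an interval chosen late, therefore leans toward the conclusion the sponsor expects (10.1.2).

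**Working it through.** **Step 1. Sample size used.** Section 10.1.2 gives 17 per arm, and 17 × 1.10 = 18.7, so 19. The target power is not stated. Assuming 80% power and 6/62 = 0.0968 against 0.50, the unpooled formula gives [0.0968 × 0.9032 + 0.25] × (1.960 + 0.842)² / 0.4032² = 16.29, so 17. This calculation concerns adverse events, not Oxford grades. I take only n = 17 from it.

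**Step 2. Does the assigned test ignore order?** Take a hypothetical table of grades 0/I/II: 12/4/1 against 5/6/6.

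- Expected counts per arm are 8.5, 5 and 3.5. X² = 2 × (3.5²/8.5 + 1²/5 + 2.5²/3.5) = 6.85 on 2 df, p = 0.032. One expected count is below 5, so the plan uses the exact test: p = 0.032.
- Mann-Whitney (tie-corrected): p = 0.010.
- Swap the first two columns. The exact p stays at 0.032, while Mann-Whitney moves to 0.54.

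**Step 3. A difference with null zero.** Over the 17 × 17 = 289 pairs, the second arm is higher in 6 × 12 + 6 × 16 = 168 and lower in 5 × 5 + 6 × 1 = 31. P(higher) − P(lower) = 137/289 = 0.47. The probabilistic index is 0.737 (95% CI 0.554 to 0.863, DeLong variance on the logit scale). Doubling and subtracting 1 gives 0.11 to 0.73. After the swap the measure is (116 − 83)/289 = 0.11, with CI −0.27 to 0.47. It therefore fits the existing zero-based rule and responds to order.

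**Step 4. Power on assumed distributions.** Simulation at 17 per arm, two-sided 0.05. The planned rule is Pearson, or exact Fisher if any expected count is below 5. Assumptions: baseline grade I in 25%, and latent correlation r between baseline and later grade. There were 40,000 trials per cell (15,000 for the large shift). Entries are power in %, planned rule then Mann-Whitney, with the gain in brackets.

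| Shift, later grades in % | Change, r = 0 | Change, r = 0.5 | Change, r = 0.8 | Visit grade |
|---|---|---|---|---|
| Large: 70/20/10/0 v 30/30/25/15 | 43.4, 65.7 (22) | 57.2, 80.2 (23) | 76.5, 90.6 (14) | 56.4, 75.5 (19) |
| Mild: 80/20/0 v 60/30/10 | 12.5, 19.0 (6) | 18.3, 28.2 (10) | 29.2, 43.7 (15) | 15.7, 27.3 (12) |
| Grades 0 and I only: 80/20 v 40/60 | 38.0, 45.1 (7) | 46.0, 57.4 (11) | 56.1, 73.1 (17) | 69.5, 69.8 (0) |

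The last row carries a warning. Mann-Whitney on change against the planned test on visit grades is 45.1 − 69.5 = −24 points at r = 0, −12 at r = 0.5 and +4 at r = 0.8. Choosing the scale can matter as much as choosing the test.

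**Step 5. The score.** Table 2 has a total with maximum 15; 7.4.4.5 and annex 16.3 have one corneal grade with maximum 5. Three areas graded 0 to 5 would total 15, but that is an inference and no areas are named. Section 7.5.8.2 mentions inspecting the conjunctiva, then refers staining back to 7.4.4.5. No conjunctival grade is available to add.

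**The case against.** The strongest reply is that the plan is incomplete here rather than unworkable. A reader might infer that this endpoint can reach neither planned conclusion. The documents do not support that: 10.3.1 reports ordinal results as proportions and promises a CI for differences, and a difference in proportions has null zero. What is missing is the cut-off or measure.

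A reader might also infer a large, established loss of power. That does not follow either. No grade distribution is documented, sparse tables go to Fisher rather than Pearson, and subjects enter at grade 0 or I, so a shift confined to those grades is realistic. There the gain on visit grades is nil, and switching to change scores can cost power.

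Nor do two listed visits show an inflated false-positive rate. The plan has no rule letting either visit decide; it simply does not name one.

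Two smaller points stand. The 0-15 text sits in a reference-value column, while entry criterion, recording and annex all use the single grade, so that part is a reconciliation of wording. And a Mann-Whitney p paired with a separately derived interval can occasionally disagree, so the interval method should be named too.

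**Conclusion.** The point holds on the text, as a specification gap that should be closed before data are seen. The assigned between-arm test does not use grade order, the interval half of the decision rule lacks a named measure, and the described score cannot be computed from what is recorded. These findings do not depend on any assumed distribution.

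The power figures do. They rest on invented grade distributions, 25% baseline grade I and a latent-correlation model, and show direction and rough size only. The practical consequence is limited: marked staining reaches the adverse-event record at grade III, so mainly smaller shifts depend on this analysis. The sample size is unaffected.

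**What to change.** 1. In Table 2 and 10.3.2.1, compare the recorded corneal Oxford grade between arms with Mann-Whitney. State in advance whether it is applied to change from baseline or to the grade at the visit.
2. Report P(PRO-231 higher) − P(PRO-231 lower) with its 95% CI, naming the interval method. The null is 0, so the rule in 3.2 and 10.3.1 stays as written. If no eye changes, report counts. Use the same measure for visual acuity and the comfort index when they fall to Mann-Whitney.
3. Name day 3 or day 8 as the deciding visit for this row.
4. Limit McNemar to a stated within-arm dichotomy, or remove it.
5. Reconcile Table 2, Table 5, 7.4.4.5 and annex 16.3 so that the analysed score is the recorded one.

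The cost is wording plus one interval per visit. No subjects or visits are added, and no measurements if the corneal grade is kept. If the sponsor wants conjunctival staining analysed, a conjunctival grade must be added to 7.4.4.5 and the eCRF.
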